9.0. RANDOMIZATION & STUDY DRUG ADMINISTRATION

9.1. Randomization: After initial assessments, participants are randomized to double-blinded Phase 1 drug assignment (escitalopram or placebo). As our primary interest for Phase 1 is related to escitalopram response, we will allocate participants in a 2:1 drug-to-placebo ratio. Randomization will be conducted by the Vanderbilt Investigational Drug Service. Nondepressed individuals will not be randomized to study drug.

Randomization will be stratified by MRI measures of total cerebral WML volume. Our measurement of total WML volume is automated and available within 24 hours of the scan and subjects will be stratified as "high" or "low" total cerebral WML volume. Based on pilot data, we will use a cutoff of 3.86mL; this is the median 3T WML volume from a cohort of 145 depressed elders analyzed using our WML segmentation method. When we reach 50% enrollment, we will re-assess this cutoff based on study data and adjust if necessary.

If there are delays in scan processing, stratification will be determined using the Coffey-modified Fazekas visual rating scale (2), dichotomizing participants as "high" (2 or 3, confluence of foci) or "low" (0 or 1, absent or punctate foci).

MRI measures will only be used for stratification. They will not guide or determine treatment decisions.

9.2. Phase 1: Blinded Escitalopram or Placebo: We selected escitalopram due to its tolerability, ease of dosing, and lack of effects on dopamine and norepinephrine (115). The Vanderbilt IDS will prepare over-encapsulated escitalopram and matching placebo and maintain the blinded assignment in case of emergencies. Participants will receive one tablet (10mg or placebo) for at least 2 weeks. If tolerated, it can be increased to a target dose of two tablets (20mg) daily at the two-week study contact, but dosing changes will not be made at week 6 or later. For problems with tolerability, the dose can be reduced to the previous level, but not below one tablet daily.

9.3. Transition: After 8 weeks subjects will be assessed for remission (MADRS \leq 7). Those achieving remission will end their study participation. Those who are not remitted will have their Phase 1 drug tapered over a week to decrease the chance of discontinuation syndrome then progress to Phase 2.

9.4. Phase 2: Bupropion XL: We selected bupropion due to its distinct mechanism of action: a norepinephrine /dopamine reuptake inhibitor with no effect on serotonin (116,117). Bupropion is safe and effective in elderly populations (118-120). Subjects will receive open-label bupropion XL starting at 150mg daily. If tolerated, after 1-2 weeks it will be increased to 300mg daily. The dose may be further increased to the maximum of 450mg daily at week 4; this dose will be reduced if needed for tolerability. Subjects not tolerating the 300mg dose will be withdrawn.

Table 1. Cognitive Domains & Tasks (21)

Episodic Memory (Alpha = 0.76)
• Word List recall; Logical memory; Constructional praxis; Benton Visual Retention Test
Executive Function (Alpha = 0.73)
• Verbal Fluency; Trail Making Test, Part B; Stroop, color-word interference; Mattis DRS, Initiation-Perseveration subscale; Wisconsin Card Sorting Test
Language Processing (Alpha = 0.62)
• Shipley Vocabulary Test; Boston Naming Test; Stroop, word reading
Processing Speed (Alpha = 0.69)
• Symbol-digit Modality Test; Stroop, color naming; Trail Making Test, Part A
Working Memory (Alpha = 0.68)
• Digit Span, forward; Digit Span, backwards; Ascending Digits

Although bupropion is often used for augmentation (121-123) for Phase 2 we decided to use it as *monotherapy*. This is supported by STAR*D data (124) that found no clear preference for augmentation versus switch strategies (125). This will simplify interpretation of Aim 2 data.

Bupropion xl may be obtained through the Vanderbilt investigational pharmacy and provided to subjects. Alternatively, the study doctor will provide a prescription and they may obtain it through their regular pharmacy. In this case, they will be instructed to save their receipts so they can be reimbursed for their cost.

9.5. End of study medication procedures: For subjects who wish to continue on their end-of-study drug, we will provide prescriptions and assist with follow-up. If they do not wish to continue on study drug, we will make referrals and work with that provider to safely taper the study drug. See Human Subjects for more detail.

9.6. Concomitant treatment: To enhance generalizability, most nonpsychotropic medications will be permitted. Concomitant psychotherapy will not be allowed as it is an effective treatment that contributes to remission through different mechanisms. We allow short-acting hypnotics (eszopiclone, zolpidem, or zaleplon) for sleep and lorazepam up to 2mg daily for anxiety. Hypnotics will be discouraged the day of cognitive testing.

9.7 Antidepressant Washout: If potential subjects are currently taking an antidepressant, they may need to come off that antidepressant in order to participate. In order to qualify to have the current antidepressant stopped, participants will need to have continued significant depressive symptomatology (MADRS \geq 15) despite taking a therapeutic dose of their current antidepressant for at least 6 weeks. The therapeutic dose will be drug specific, but equivalent to fluoxetine 20mg (such as sertraline 50mg or escitalopram 10mg, for example). Individuals who responded to their antidepressant and do not have this level of depressive symptom severity will not be enrolled in the study and will not be tapered off their medication. The medication taper will occur over 1-3 weeks, dependent on the drug, dose, and duration. They will be assessed with weekly telephone visits during this period to monitor for depression worsening.

9.8. Source of Study Drug: The Vanderbilt Investigational Drug Service will provide study drug for both Phase 1 and Phase 2 for all participants aside from Veterans who receive care at the VA TVHS. Veterans will receive study drug from the VA TVHS Research Pharmacy. The Vanderbilt IDS will coordinate with the VA TVHS Research Pharmacy to assure accuracy in study drug assignment for Phase 1.

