12.0. POTENTIAL RISKS

1. **Interview, emergencies, and possible suicidal ideation.** Subjects may experience discomfort during the clinical interview and evaluations when discussing symptoms, life events, and social support. The Project Coordinator will be experienced and skilled in interviewing depressed subjects. Should the subject wish to stop or take a break, the coordinator will allow it. A study doctor will be available as a backup. In addition, should the subject express suicidal ideation at any time during the interview, a study doctor will be contacted immediately to assess the subject and to determine the appropriate course of action. Thoughts of suicide will be taken very seriously. Options for addressing this may include contacting the individual's mental health caregiver, referring for urgent evaluation and treatment, or emergent evaluation and hospitalization. Similar practices will be used for other emergencies, including but not limited to psychosis, homicidal or violent thoughts, or an acute change in a subject's physical status.
2. **Unblinding:** It is possible that it may be crucial to definitively identify what study drug a participant is receiving to provide optimal care. We will only break the blind if knowledge of the study drug in Phase 1 (escitalopram or placebo) is necessary to provide optimal treatment in an emergency situation. If the emergency situation is an adverse event, this will be recorded and reported as such. Emergency unblinding will be conducted through the Vanderbilt Investigational Drug Service, who is providing study drug and blinding procedures. They have 24-hour access for emergency unblinding.
3. **Antidepressant Side Effects:** We will formally assess side effects at each planned contact and informally as needed through additional or unscheduled calls. We will attempt to minimize side effects by slow titration and allowance for dose reduction if needed. We will withdraw subjects from the study if they cannot tolerate the lowest dose of 10mg of escitalopram or placebo equivalent during phase 1 or 150mg of bupropion xl during phase 2.

We describe below some of the more common or particularly concerning side effects. There is always the potential for the development of rare, unanticipated side effects. In general, we will carefully assess subjects with new complaints to determine if they may be related to study drug and if there is a need for closer monitoring or change in study drug dosing.

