- a. **Escitalopram common side effects:** Although generally well tolerated, escitalopram does carry risk of side effects. These include: dermatological (rash), gastrointestinal (dry mouth, nausea, diarrhea, constipation), neurological (dizziness, vivid dreams), systemic (fatigue, somnolence or insomnia, appetite change, weight loss/gain, sweating), and sexual dysfunction.
 - b. **Bupropion common side effects:** Likewise, bupropion is generally well tolerated. Common side effects include: dermatological (rash), gastrointestinal (nausea, diarrhea, constipation, dry mouth), neurological (dizziness, headache, tinnitus, tremor, vivid dreams), psychiatric (anxiety, agitation), or systemic (insomnia, appetite and/or weight loss, sweating). There are also rare risks of seizures or Stevens-Johnson syndrome, which we address through our entry criteria.
 - c. **Suicide risk:** Antidepressant-induced suicidality is an important concern and one that has resulted in a black-box warning on antidepressants by the FDA. We will both inform subjects of this potential risk and monitor for suicidality at each contact. Should any possible suicidality be detected, a study doctor will assess that individual and act accordingly (see Item 1 above).
 - d. **Discontinuation Syndrome:** Discontinuation syndrome, seen with abrupt cessation of antidepressant drugs, may cause a variety of neurological (dizziness, vertigo, insomnia, tremor, paresthesias), gastrointestinal (nausea, abdominal cramping), systemic (lethargy, flu-like symptoms) and psychiatric symptoms (irritability, anxiety, dysphoria). We will provide a medication taper for individuals who wish to stop escitalopram at the study's end.
4. **Risk of Placebo:** The primary concern with use of placebo is that individuals receiving placebo will fail to improve or worsen over the course of the placebo period. We minimize this risk by using a shorter study (8

weeks in contrast to 10 or 12 weeks) and use of withdrawal criteria, including worsening depression (“stopping rules” – see Section 12 below). We further minimize this risk by an unequal allocation of subjects in phase 1 to escitalopram or placebo in a 2:1 ratio. Such an approach is feasible as we are not testing for drug efficacy but examining neural predictors of remission, which we hypothesize would differ between escitalopram and placebo.

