5. Antidepressant Medications: End of Study Procedures: During the course of the study we will work with study subjects to identify providers who will continue their care at the end of the study. For those subjects who wish to continue on their end-of-study drug, we will provide prescriptions, two free visits, and assist with arranging follow-up clinic visits with their provider. If they do not wish to continue on study drug, we will also refer to clinical providers, but also work to slowly discontinue the study drug to avoid discontinuation effects.
6. Magnetic Resonance Imaging. Although this procedure is generally low-risk, there are particular concerns. Individuals will be screened for the presence of implanted metal (including but not limited to medical devices, shrapnel, tattoos or permanent makeup); those who screen positive will be excluded from the study. Claustrophobia is also an issue for many potential subjects. During the MRI, subjects will have voice contact with a radiology technician, and may request the scan be stopped at any time.
7. Incidental Findings: Magnetic Resonance Imaging: Another risk is the occurrence of incidental findings on MRI. All scans are reviewed at time of acquisition and concerning findings are discussed with an attending neuroradiologist. Should any concerning findings be seen, a study doctor will convey these findings to the subject along with recommendations for further evaluation, and facilitate referrals for such evaluation and treatment.
8. Breach of confidentiality: There is the potential risk of breach of confidentiality of clinical, genetic, and laboratory information. The PI, [name], has extensive experience as a clinical investigator dealing with such sensitive information, and as a previous member of an Institutional Review Board has experience assuring that data is adequately protected. Safeguards to protect confidentiality include locked records and firewalls around password-protected electronic data, and all study data being coded, with the key linking the code with a subject’s identity being kept in a separate, locked file.

13.0. ADVERSE EVENT REPORTING:

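### Phase 1 remitters exit on blinded drug with the offer of a prescription to continue it, but the protocol has no non-emergency route to the assignment

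*Combined protocol and SAP*

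**What the plan says.** **Blinding.** Phase 1 is double-blind (section 9.1), and "we will allocate participants in a 2:1 drug-to-placebo ratio". Under section 9.2 the Vanderbilt Investigational Drug Service prepares over-encapsulated escitalopram and matching placebo, and its task is to "maintain the blinded assignment in case of emergencies".

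**Exit at week 8.** Section 9.3 sends non-remitters, after a one-week taper, to open-label bupropion. For remitters (MADRS 7 or below) it says: "Those achieving remission will end their study participation".

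**Prescription at exit.** Section 9.5: "For subjects who wish to continue on their end-of-study drug, we will provide prescriptions and assist with follow-up". Section 12.0 item 5: "For those subjects who wish to continue on their end-of-study drug, we will provide prescriptions, two free visits", plus help in arranging follow-up. Neither limits the offer to people leaving from Phase 2.

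**Unblinding.** Section 12.0 item 2: "We will only break the blind if knowledge of the study drug in Phase 1 (escitalopram or placebo) is necessary to provide optimal treatment". The sentence goes on to restrict this to an emergency.

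**Taper at exit.** Section 12.0 item 3d: "We will provide a medication taper for individuals who wish to stop escitalopram" when the study ends.

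**The concern.** The conflict lies on the ordinary route of a participant who does well in Phase 1. That person never reaches the open-label phase, so the end-of-study drug is the blinded capsule. The protocol offers a prescription for it and keeps from the prescriber what it is.

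For someone who remitted on escitalopram, a prescription for escitalopram is continuation. For someone who remitted on placebo, the same prescription begins a drug that the person has not been taking in the trial, after scheduled study assessments have ended. With the assignment sealed, neither the prescriber nor the participant can tell these cases apart. The protocol does not say what should happen, so staff would have to settle it case by case.

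**Working it through.** The protocol states no figure to reproduce. The main check is whether the rules can be followed together, and the counts only show scale.

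**Consistency of the rules**

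1. *What is the end-of-study drug of a Phase 1 remitter?* By sections 9.2 and 9.3, over-encapsulated escitalopram or matching placebo, because participation ends before Phase 2.
2. *Is such a person covered by the offer?* Yes. Sections 9.5 and 12.0 item 5 address anyone who wishes to continue.
3. *Can the prescriber learn the assignment?* Item 2 allows this only in an emergency, and a routine exit prescription is not one. The other access to unblinded data is in section 13.0: the independent safety monitor may request it if adverse event rates cause concern. That does not reach a prescriber.
4. *Is there an exit disclosure step?* None appears in sections 9.3, 9.5, 12.0 or 14.0.
5. *Does the problem extend to Phase 2?* No. Bupropion is open-label, so the offer works there as written.
6. *Is remission on placebo expected?* Yes. Section 11.4 plans to compare interval change between those who remit on drug and those who remit on placebo.

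**Scale**

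Inputs: 130 evaluable depressed participants (section 4.0); 2:1 allocation (section 9.1); base non-remission of 0.36, hence remission of 0.64 (section 15.1). Section 15.1 does not tie the 0.36 to an arm. I apply it to escitalopram for illustration. The placebo remission rate is not given, and I assume 20% to 64%, the upper end being equal remission in both arms.

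- Placebo: 130 × 1/3 = 43.3. Escitalopram: 130 × 2/3 = 86.7.
- Escitalopram remitters: 86.7 × 0.64 = 55.5.
- Placebo remitters = 43.3 × assumed rate; share = placebo remitters / (placebo remitters + 55.5).

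| Assumed placebo remission | Placebo remitters | Share of all Phase 1 remitters |
|---|---|---|
| 20% | 8.7 | 13.5% |
| 30% | 13.0 | 19.0% |
| 40% | 17.3 | 23.8% |
| 50% | 21.7 | 28.1% |
| 64% | 27.7 | 33.3% |

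So about 9 to 28 placebo remitters would leave at week 8. These are upper counts, because only those who wish to continue are affected.

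**The case against.** **The offer can be kept without unblinding.** A reader might infer that the promise is impossible to honour. The documents do not support that: open-label escitalopram could be prescribed to any remitter with the blind intact, and for those on active drug that would be continuation. For a placebo remitter, however, it would be a new start, and the protocol neither describes nor acknowledges this course.

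**Item 2 may govern only care during the study.** It speaks of the drug a participant is currently receiving and of round-the-clock emergency access, so it could be read as silent about exit. That reading is open, but the word only has no such limit. Even on that reading the protocol would still lack an exit procedure.

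**The detail may be elsewhere.** Section 9.5 points to a Human Subjects text. No section here bears that title, and consent pages are not in the copy reviewed. The closest counterpart, section 12.0 item 5, repeats the offer without settling the matter. A separate document could hold a procedure. If so, the protocol should cite it.

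**Follow-up continues after exit.** This stands in part. Sections 12.0 and 14.0 offer two free visits, so it would be wrong to say that all contact ends. Scheduled study assessments do end.

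**A taper does not need the assignment.** This largely stands. Section 9.3 tapers Phase 1 drug for non-remitters with no unblinding step. A reader might take item 3d as a second contradiction of equal weight. It is a lesser wording point: it offers the exit taper by drug name, which presumes that the drug is known.

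**Biased ratings.** A reader might infer that assignments will leak and bias the MADRS or the arm-by-tract interaction in Aim 2. That requires an informal breach of item 2, which nothing in the documents suggests. A remitter's week-8 score is already recorded by then, one completed participant's arm does not reveal another's, and section 16.0 gives image analysts coded identifiers only. No bias is shown.

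**Conclusion.** The point holds as a conflict between stated rules. Sections 9.3, 9.5 and 12.0 items 2 and 5, taken together, leave the prescriber unable to tell continuation from a new drug start for Phase 1 remitters who wish to continue. Phase 2 completers are not affected.

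The uncertainty covers every Phase 1 remitter who asks to continue. The mismatch itself arises only for those on placebo: at most about 9 to 28 people, or 14% to 33% of Phase 1 remitters. That range rests on 130 evaluable participants, 2:1 allocation, the assumed 20% to 64% placebo remission and, for the percentages, 64% remission on escitalopram. The conflict does not depend on these figures.

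This should be corrected because it recurs in the normal conduct of the trial and is cheap to resolve. It does not threaten the Aim 1 or Aim 2 analyses.

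**What to change.** Reconcile sections 9.3, 9.5 and 12.0 items 2, 3d and 5 so that the protocol states how a Phase 1 remitter's assignment is handled at exit, and resolve the pointer in section 9.5. Whether such a participant continues, stops or tapers, and on what, is for the sponsor and investigator to decide.

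If they choose disclosure, the conduct side could read as follows:

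- Amend the word only in item 2 to allow a planned, logged, non-emergency release for Phase 1 remitters.
- Release comes from the dispensing pharmacy, including the VA TVHS Research Pharmacy that supplies Veterans under section 9.8.
- Release follows the week-8 MADRS and any repeat MRI under section 11.4.
- The assignment goes to whoever writes the exit prescription and not to MADRS raters or image analysts. Sections 9.5 and 12.0 item 5 say that the study team provides the prescriptions, so release to an outside provider alone would not be enough.

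The cost is protocol wording and a pharmacy procedure. The downside is a small risk that assignments of completed participants leak to site staff. Sample size and analysis are unchanged.

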10.0 CLOSED - LONG-TERM FOLLOWUP (SUB-STUDY)

The long-term follow-up substudy is now closed. Depressed individuals who were randomized were asked to enter long-term follow-up over the next year. This included only minimal-risk interviews and questionnaires occurring 6-months and 12-months after study exit. This did not affect clinical treatment decisions over this period. The goal of this exploratory sub-study was to gather data on long-term rates of depression relapse. We examined whether neuroimaging measures obtained at baseline or clinical measures obtained throughout the study are related to subsequent rates of relapse over the one-year follow-up period.

10.1. Consent: We discussed this optional sub-study at their final study visit. Those who were agreeable were asked to sign a separate sub-study consent form.

10.2. Procedures: This only involved a telephone interview and completion of study questionnaires at 6- and 12-months after study completion. The telephone interview included an assessment of current medication use with the ATHF and depression severity using the MADRS. During the interview we worked to identify the duration of time they experienced clinically significant depressive symptoms over the interim, particularly for those individuals who remitted through the study but later experienced a relapse of depression. The telephone interview was followed by a completion of study questionnaires assessing depressive symptoms – these are listed in Section 7.1.d above.

10.3. Safety: For any participants who are depressed at either assessment, we assured that they were currently receiving treatment for their depression. If so, we encouraged them to let their physician know about their symptoms. If they were not, we provided referral recommendations, including a referral to the Vanderbilt Psychiatry Outpatient Clinics. As we make these referrals at the end of the main study, we did not anticipate that many individuals will be without treatment.

We also assessed for thoughts of death or suicide as part of measuring depression severity with the MADRS. A study physician then assessed the safety of anyone endorsing these thoughts and acted as was clinically indicated. This may have included feedback to the patient's treating psychiatrist or referrals to

intensive outpatient or inpatient hospitalization.

